7.8 Description of Known Adverse Event Profile for ACAM2000

The following information has been described within a 'black box warning' for ACAM2000; for complete information on the known AE profile of ACAM2000, see the *Investigator's Brochure*.

- Suspected cases of pericarditis and/or myocarditis have been observed in healthy adult primary vaccinees (at an approximate rate of 5.7 per 1000, 95% CI: 1.9 to 13.3) receiving ACAM2000.
- Encephalitis, encephalomyelitis, encephalopathy, progressive vaccinia, generalized vaccinia, severe vaccinia skin infections, and erythema multiforme major (including STEVENS-JOHNSON SYNDROME) and eczema vaccinatum resulting in permanent sequelae or death, ocular complications, blindness, and fetal death have occurred following either primary vaccination or revaccination with live vaccinia virus smallpox vaccines.

These risks are increased in vaccinees with the following conditions and may result in severe disability, permanent neurological sequelae and/or death:

- Cardiac disease or a history of cardiac disease
- Eye disease treated with topical steroids
- Congenital or acquired immune deficiency disorders, including those taking immunosuppressive medications
- Eczema and persons with a history of eczema or other acute or chronic exfoliative skin conditions
- Infants less than 12 months of age
- Pregnancy

ACAM2000 is a live vaccinia virus that can be transmitted to persons who have close contact with the vaccinee and the risks in contacts are the same as those for the vaccinee.

The risk for experiencing serious vaccination complications must be weighed against the risks for experiencing a potentially fatal smallpox infection.

In addition to the boxed warning common adverse events associated with ACAM2000 are those expected following vaccinia vaccination, including inoculation site signs and symptoms, lymphadenitis, and constitutional symptoms, such as malaise, fatigue, fever, myalgia, and headache. These adverse events are less frequent in revaccinated persons (due to pre-existing immunity) than in primary vaccinees.

Inadvertent inoculation at other sites is the most frequent complication of vaccinia vaccination. The most common sites involved are the face, nose, mouth, lips, genitalia and anus. Self-limited skin rashes not associated with vaccinia replication in skin, including urticaria and folliculitis, may occur following vaccination.

7.8.1 Anticipated Vaccine Reactogenicity and Adverse Events

The expected responses to re-vaccination with ACAM2000 are similar to the expected responses of primary vaccinia vaccination, except typically with less severity and shorter duration. In general, the shorter the interval between first-time vaccination and revaccination, the more likely it is that there will be no "take" or major reaction. Among those for whom 25 years or more has elapsed since last vaccination, essentially all should experience a "major reaction" indicative of a vaccination "take". Rarely, in some individuals, seemingly appropriate vaccination techniques may result in no reaction; these are considered as 'non-takes'.

The expected responses to vaccination "take" include:

- Reddening of the injection site within 30 minutes of administration.
- The development of a papule at the site of vaccination two to five days after percutaneous administration of vaccinia vaccine.
- The papule becomes vesicular, then pustular and reaches its maximum size in eight to ten days.
- The pustule dries and forms a scab, which separates within 14 to 21 days, leaving a scar.
- Local reactions at the inoculation site are expected, including redness, swelling, tenderness, pain and itchiness.
- Fever (approximately 15% of vaccinees are expected to develop a fever >100°F upon re-vaccination).

These reactions are typically mild ([Table 1](#)) and do not interfere with daily function. Any clinical observation that fit these criteria will not be characterized as adverse events.

Variations of expected reactions may occur in a small number of vaccinees including:

- Local satellite lesions (that are normal in appearance) and are within 2.5 cm (1 inch) of the vaccination site
- Lymphangitis
- Local edema
- Robust "take" (intense inflammation surrounding the papule)

None of these expected variations of normal reactions require any treatment other than symptomatic relief ([7](#)).

However, if an expected vaccine reaction is of greater intensity or duration (i.e., moderate or severe pain ([Table 1](#)), requires medication or interferes with daily life), these observations should be characterized as an adverse event.

Regardless of whether these observed vaccine site reactions are characterized as adverse events or not, the clinical observation should be noted in the donor record file.

If study subjects are diagnosed with complications of vaccinia vaccination that are treatable with VIGIV (eczema vaccinatum, progressive vaccinia, ocular vaccinia resulting from inadvertent implantation, or severe generalized vaccinia), refer to section 7.8.2 on how to obtain VIGIV from the CDC for treatment of these complications and sections 7.9 and 7.10 for reporting requirements.

7.8.2 Treatment of Complications of Vaccinia Vaccination

The only product currently approved for the treatment of complications of vaccinia vaccination is VIGIV. VIGIV is an isotonic sterile solution of the immune globulin fraction of plasma from persons vaccinated with vaccinia vaccine. VIGIV is indicated for treatment of the following complications of smallpox vaccination:

- Eczema vaccinatum
- Progressive vaccinia
- Severe generalized vaccinia
- Vaccinia infections in individuals who have skin conditions such as burns, impetigo, varicella-zoster, or poison ivy, or in individuals who have eczematous skin lesions because of either the activity or extensiveness of such lesions
- Aberrant infections induced by vaccinia virus that include its accidental implantation in eyes (except in cases of isolated keratitis), mouth, or other areas where vaccinia infection would constitute a special hazard

VIGIV must be administered as per the VIGIV Package Insert and should be administered as early as possible after the onset of symptoms.

The CDC is the only source of VIGIV for civilians. Please contact: the CDC Director's Emergency Operations Center (DEOC) at [contact] should any vaccination complications arise that would necessitate treatment with VIGIV. This number is accessible 24 hours a day, seven days a week.

Note: If complications of vaccinia vaccination develop requiring treatment with VIGIV, these should be recorded and/or reported to Emergent as described in section 7.10 and to CDC and/or Local/State Health Authorities as described in section 7.8.

7.9 Adverse Event/Reaction Reporting

The following are adverse events of special interest that need to be reported to the sponsor's Pharmacovigilance department by phone (see section 7.10) within 24 hours of knowledge of the event: autoinoculation, cardiomyopathy, central nervous system disease, contact transmission of vaccinia, death, eczema vaccinatum, fetal vaccinia, generalized vaccinia, ischemic heart disease, ocular vaccinia, potential myocarditis and pericarditis, progressive vaccinia, Stevens-Johnson Syndrome, and superinfection of vaccination site.

Occurrence of adverse events will be reported into the eCRF and monitored throughout all phases of the study at all visits and will cover all participating subjects. Study subjects will be provided with a 24-hour telephone number to contact study personnel in case of an untoward reaction.

The Principal Investigator(s) will follow all adverse events for at least four weeks after the administration of ACAM2000 and throughout all phases of the study up to the final study visit. The related adverse events will be followed until resolution or stabilization as applicable.

According to CDC Reporting Guidelines (8) "Any adverse reaction that requires treatment with VIGIV should be reported immediately, and adverse events that meet the regulatory criteria for "serious" (i.e., those resulting in hospitalization, permanent disability, life-threatening illness, or death) should be reported within 48 hours; all other events should be reported within 1 week by the Principal Investigator." Vaccinia complications, including those in section 7.8.2, are also reportable to CDC.

If smallpox vaccination/vaccinia-related AEs are required to be reported to the site's State or Local Health Authority(ies), the Principal Investigator will be responsible for such reporting. If a complication arises, such as a second scab or satellite lesions close to the vaccination site, these AEs may not be considered reportable. The complications that arise within the area under the bandage can be handled according to instructions in this protocol for vaccination site care. Such expected vaccination reactions may only be considered reportable at the investigator's discretion considering subject and close contact safety, specifically the risk of vaccinia spread to self or others. Please review your site's relevant State and Local Health Authority reporting requirements as most states require reporting immediately or within 24 hours.

[figure not shown]
7.10 Reporting of Serious Adverse Events/Reactions and Adverse Events of Special Interest

The healthcare provider/investigator will report all SAEs, including deaths, and adverse events of special interest (AESI) to Emergent by phone within 24 hours of knowledge of the event. A completed SAE Form must be submitted to the sponsor (including medical summary of the SAE and AESI) within three calendar days of the physician or healthcare provider's knowledge of occurrence of the SAE or AESI.

Emergent will contact the investigator (or designee) for the SAE or AESI follow-ups.

All reports should be made to:

[REDACTED]
[REDACTED]
[REDACTED]
[REDACTED]
[REDACTED]

Emergent will report all unexpected Serious Adverse Reactions (SARs) to the Central Institutional Review Board (IRB) that would be responsible for the study and to the appropriate regulatory agencies according to established regulatory reporting guidelines. Emergent will also report Serious Adverse Reactions (SARs) to the DSMB according to the terms of the DSMB Charter.

All clinical site investigators will be notified of the occurrence of any SAEs considered related to product exposure at other investigational sites.

7.11 Unanticipated Problems

As outlined by the Office for Human Research Protection (OHRP), unanticipated problems must be reported to the IRB according to the requirements of 45 CFR Part 46. Unanticipated problems are considered to include any incident, experience, or outcome that meets all of the following criteria:

[figure not shown]
- Unexpected (in terms of nature, severity, or frequency) given:
 - Procedures that are described in the study-related documents, such as the IRB approved research protocol and informed consent document.
 - The characteristics of the subject population being entered into the study.
- Related or possibly related to participation in the study which means there is a reasonable possibility that the incident, experience, or outcome may have been caused by the sample collection.
- Suggests that the study places subjects or others at a greater risk of harm (including physical, psychological, economic, or social harm) than was previously known or recognized.

An incidence, experience, or outcome that meets the three criteria above generally will warrant consideration of substantive changes in the study or informed consent process document or other corrective actions in order to protect the safety, welfare, or rights of subjects or others. Only a small subset of AEs occurring in human subjects participating in study will meet these three criteria for an unanticipated problem. There are other types of incidents, experiences, and outcomes that occur during the conduct of human subject trials that represent unanticipated problems but are not considered AEs. For example, some unanticipated problems involve social or economic harm instead

of the physical or psychological harm associated with AEs. In other cases, unanticipated problems place subjects or others at increased risk of harm, but no harm occurs.

Below (Figure 1) is a flow chart to determine whether an adverse event represents an unanticipated problem that needs to be reported under the DHHS regulations at 45 CFR part 46.

Figure 1 Determination of AE Reporting under 45 CFR part 46

Upon becoming aware of any other incident, experience, or outcome (not related to an adverse event) that may represent an unanticipated problem, the Principal Investigator should assess whether the incident, experience, or outcome represents an unanticipated problem by applying the criteria for assessment of unanticipated problems described above. If the investigator determines that the incident, experience, or outcome represents an unanticipated problem, the investigator must report it promptly to the IRB.

7.12 Risks and Discomforts

During the vaccination the subject may experience pain and/or bruising at the needle entry site.

8 STATISTICAL ISSUES IN STUDY DESIGN AND ASSESSMENT

8.1 Sample Size Calculation

Approximately 750 to 3000 plasma donor subjects will be enrolled. Plasma will be collected from a sufficient number of subjects vaccinated with ACAM2000 to produce enough plasma needed to manufacture VIGIV for the current contracts.

8.2 Interim Analyses

Safety information will be collected and tabulated in the form of related AEs, which will be reported annually to the Central IRB according to the IRB reporting policies. Expedited Reports are submitted to the IRB as required.

8.3 Planned Method of Analyses

The final study report will include tabulated data collected from subjects' eCRF. Adverse events will be coded using the MedDRA coding dictionary and will be listed and summarized. Summary of adverse events by relatedness will be based on the final Sponsor's causality assessment. Adverse events assessed as Definitely, Probably or Possibly Related will be considered as 'related' to the study drug (i.e., adverse reactions).

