3.4 Criteria for Stopping or Terminating the Study

Emergent and the Principal Investigator may elect to terminate the study early as defined by the clinical study agreement. The study may be terminated at any or all sites for any of the following reasons:

- The safety data demonstrate or strongly suggest that the study treatment (or participation in the study) is unsafe. The Principal Investigator and sponsor, with input from the DSMB, will be responsible for ongoing review of safety data. The Principal Investigator will initially assess seriousness, causality and intensity (severity) of an adverse event.
- The protocol or conduct of the study is flawed such that the safety or rights of the study subjects may be adversely affected.
- The ethics committee has withdrawn the approval for the study and has denied reconsideration.
- Sponsor agrees with DSMB recommendation for stopping, terminating or suspending the study based on DSMB Charter.
- Poor recruitment.
- Relocation of the Principal Investigator or reallocation of Principal Investigator's responsibilities, or disqualification of the Principal Investigator by order of the regulatory authority.
- Non-adherence to the protocol or unavailability of the Principal Investigator or his/her staff for the sponsor's (or their authorized representative) monitoring personnel.
- Inadequate evidence of the Principal Investigator's personal conduct or supervision of the study.
- Change of research strategy or change of management priorities.
- Imposition of clinical hold by a regulatory authority.

Any decision to voluntarily suspend or terminate a clinical study will be carefully reviewed and fully justified. The sponsor will notify the FDA and the Central Institutional Review Board (IRB) of any suspension or termination, along with justification for restarting or terminating the study as applicable.

The Principal Investigator must notify the IRB in writing of the study's completion or early termination. Emergent must receive a copy of the notification letter from the IRB indicating receipt of the completion or early termination letter.

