7 MANAGEMENT AND REPORTING OF ADVERSE EVENTS/ADVERSE REACTIONS

The Principal Investigator is responsible for the evaluation and documentation of events meeting the criteria and definition of an adverse event (AE)/adverse drug reactions (ADR) or serious adverse event/reactions (SAE/SAR) as provided in this protocol.

All AEs are to be elicited by the Principal Investigator. The causality relationship of an AE with the study drug is to be determined by Principal Investigator.

Diary cards will be utilized to help subjects record and track AEs between study assessments. All adverse events/reactions on diary cards will be reviewed with subjects by the Principal Investigator and/or designate at the regularly scheduled visits. The reviewer will sign the diary card to document this review. If unable to sign the diary card, the Principal Investigator will document review of the diary card in the corresponding visit source document. If the subject is unable to attend in person, an image of the diary card will be transmitted to the Principal Investigator by photo or live video call. If possible, an image of the diary card will be printed and filed in the subject's source document file. Adverse events from the diary card will then be entered into the electronic case report form (eCRF) that is within data capture (EDC) system.

All adverse events/reactions will be examined by the investigator for assessment of both severity and causality using the criteria described in sections [7.6](#) and [7.7](#).

The definitions for adverse events/adverse drug reactions, as well as serious events/reactions provided below follow definitions provided by ICH, 21 CFR 312 and Office for Human Research Protection (OHRP) Guidance documents.

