7.2 Adverse Drug Reaction(s) (ADRs)

An adverse drug reaction is defined as an unwanted noxious and unintended response to a therapeutic drug. ADRs are characterized by a suspected causal relationship between the product and the occurrence of the reaction.

The phrase "unwanted noxious and unintended response" means that a causal relationship between the medicinal product and the onset of an adverse event is at least a reasonable possibility, i.e., the relationship cannot be ruled out.

Causal relationships should be assessed according to section 7.7.

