7.7 Assessment of Causality

Causality is an established relationship between the occurrence of an adverse event/reaction and the concomitant or previous intake of medications.

Adverse events may be caused by one or more of the following:

1. The product and/or procedures involved in the research study.
2. An underlying disease, disorder, or condition of the subject.
3. Other circumstances unrelated to the research or any underlying disease, disorder, or condition of the subject.

In general, adverse events that are determined to be at least partially caused by (1) would be considered related to participation in the research, whereas adverse events determined to be solely caused by (2) or (3) would be considered unrelated to participation in the research.

The various causality categories are listed in Table 2.

Table 2 General Definitions of Causality Categories

Certain (Definitely Related)	
 Event or laboratory test abnormality, with plausible time relationship to the study drug intake Cannot be explained by disease or other drugs Response to withdrawal plausible (pharmacologically, pathologically) Event definitive pharmacologically or phenomenologically (i.e. an objective and specific medical disorder or a recognized pharmacological phenomenon) Rechallenge satisfactory, if necessary
Probable (Probably Related)	
 Event or laboratory test abnormality, with reasonable time relationship to drug intake Unlikely to be attributed to disease or other drugs Response to withdrawal clinically reasonable Rechallenge not required
Possible (Possibly Related)	
 Event or laboratory test abnormality, with reasonable time relationship to drug intake Could also be explained by disease or other drugs Information on drug withdrawal may be lacking or unclear
Unlikely	
 Event or laboratory test abnormality, with a time to drug intake that makes a relationship improbable (but not impossible) Disease or other drugs provide plausible explanations
Unrelated	
 No temporal association to study product. An alternate etiology has been established. The event does not follow the known pattern of response to study product. The event does not reappear or worsen with re-challenge.

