Conditional/ Unclassified ^a	
 Event or laboratory test abnormality More data for proper assessment needed, or Additional data under examination
Unassessable/ Unclassifiable ^a	
 Report suggesting an adverse reaction Cannot be judged because information is insufficient or contradictory Data cannot be supplemented or verified

^a This is a temporary assessment to be used within the initial SAE report, since stringent timelines might not allow the collection of all the information necessary for making proper causality assessment. In this case, investigators must actively seek all available data on the event and provide a causality assessment of certain (definite)/ probable/ possible/ unlikely in a follow-up SAE report.

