6 ANALYSIS METHODS

Adverse events will be coded by the MedDRA coding dictionary. The incidence, intensity and relationship of events to ACAM2000® will be evaluated through the use of frequency tables, by MedDRA system organ class and preferred term.

The adverse events causality will be reported by the principle investigator from the sites, and reviewed by the medical monitor on a monthly basis. The company assessed causality for the adverse events will be documented as part of the standard process of medical review. The

summary of adverse events by relatedness will be based on the final company causality assessment.

In order to calculate the incidence of adverse events, each subject will be counted only once within each system organ class and preferred term category. The total number of events will also be provided for each system organ class and preferred term. When intensity or relationship to ACAM2000® is considered, the subject will be counted once, within each system organ class and preferred term category, for each intensity or relatedness category.

The incidence of most common reported Adverse Events, defined as those reported by at least 5% of subjects, will be tabulated by system organ class and preferred term as described above.

All adverse events reported during the study will be listed individually by subject. The time to onset of each adverse event relative (in number of days) to the day of ACAM2000® administration (Day 0) will be provided.

Serious Adverse Events (SAEs) will be listed and summarized in the same fashion as for all adverse events, if applicable.

The assessment of peri/myocarditis symptoms will be listed individually over time, including Day 90 safety assessment.

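### Do the relatedness tables need changing because they use only the sponsor's final causality rating and not the investigator's?

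*Protocol*

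**What the plan says.** Two parties rate causality. The investigator goes first. Protocol 3.4 states: "The Principal Investigator will initially assess seriousness, causality and intensity (severity) of an adverse event". Protocol section 7 adds: "The causality relationship of an AE with the study drug is to be determined by Principal Investigator". SAP section 6 confirms the route: "The adverse events causality will be reported by the principle investigator from the sites". The medical monitor then reviews these ratings monthly, and a company assessment is documented as part of medical review.

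For the summaries, Protocol 8.3 chooses the second rating: "Summary of adverse events by relatedness will be based on the final Sponsor's causality assessment". SAP section 6 makes the same choice. Protocol 8.3 also fixes the dividing line: "Adverse events assessed as Definitely, Probably or Possibly Related will be considered as 'related' to the study drug".

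Protocol 7.7 supplies the scale: "The various causality categories are listed in Table 2". Two of its seven categories, Conditional and Unassessable, carry a footnote: "This is a temporary assessment to be used within the initial SAE report". The same footnote obliges the investigator to seek the missing data and give a definite category in a follow-up report.

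Protocol 7.2 describes an adverse drug reaction as an event for which a causal relationship "is at least a reasonable possibility, i.e., the relationship cannot be ruled out". SAP section 5 omits missing values from the summaries and uses no imputation.

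**The concern.** With no comparator arm, attribution to the vaccine rests on judgement. The plan collects two judgements and specifies its relatedness summaries on one of them, the one made after sponsor review. The data safety monitoring board (DSMB) receives the package defined in the SAP appendices. From those tables it could not tell how far the related-event rate depends on reclassification. Upgrades and downgrades that cancel out would leave the totals unchanged.

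The second worry is an event still coded Conditional or Unassessable, or left blank, at database lock. Protocol 8.3 does not count it as related, while Protocol 7.2, read loosely, suggests that an unexcluded relationship is a reaction. Because the two codes belong to serious-event reports, any such event would be a serious one. If the worry were right, the related-event rate could be understated and the reader would not know by how much.

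**Working it through.** There is no planned figure to reproduce: the study has no formal test, margin or power calculation. The check is to set the passages side by side.

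**1. Which outputs depend on relatedness?** From the titles in SAP Appendices I and III:

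| Output | Depends on relatedness? |
|---|---|
| Tables 14.3.1.2, 14.3.1.6 (only if there are enough serious events) and 14.3.1.9 | Yes |
| Listing 16.2.7.2 | Yes |
| Tables 14.3.1.1, 14.3.1.3, 14.3.1.4, 14.3.1.5, 14.3.1.7, 14.3.1.8 | No |
| 14.3.2 and 14.3.3 (deaths and serious events: listing and narratives) | No |
| Listing 16.2.7.1 (all adverse events) | No |

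Three tables and one listing are affected. Reclassifying an event moves it between rows of a relatedness table, or in or out of 14.3.1.9 and 16.2.7.2. It cannot remove the event from the all-event table or listing.

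**2. Whose rating is used?** Protocol 8.3 and SAP section 6 agree, and both speak of the summary. Neither names the assessor for listings 16.2.7.1 and 16.2.7.2. Protocol 7.1 requires causality to be collected and the event entered in the electronic data capture system, and SAP section 6 lists every event by subject. A column for the investigator's rating would fit there or in the narratives. The columns are set in the shells, which the 2019 note to the SAP mentions but which are not among the documents. Titles alone therefore cannot show that the rating is left out.

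**3. What happens to an unresolved rating?**

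| State at lock | Text that applies | Result |
|---|---|---|
| Conditional or Unassessable | Protocol 7.7 footnote | Provisional; the investigator must replace it |
| Still so coded | Protocol 8.3, three categories only | Not counted as related; can be its own row in 14.3.1.2 |
| Blank | SAP section 5 | Not imputed |

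The outcome is determinate without a dedicated sentence. The summaries also use the sponsor's final assessment, and nothing says that this assessment may carry either provisional code.

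**4. Would counting unresolved events as related be better?** Protocol 7.2 turns on a reasonable possibility. A blank or pending entry expresses no such view. If failure to exclude were enough by itself, the Unlikely category would also qualify, since Table 2 defines it as improbable but still conceivable, and Protocol 8.3 leaves Unlikely out. The rule would count an unassessed event as related while an event assessed as Unlikely was not. It would also put a worst-case imputation into the main count, against SAP section 5.

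**5. Size.** The documents give no rate of disagreement. One subject whose only related event is reclassified moves the any-related-event rate by 1/N: 1/750 = 1.33 per 1000, or 1/3000 = 0.33 per 1000. That holds in any study of this size and says nothing about how many subjects would be reclassified.

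**6. Would repeating the three tables by investigator rating answer the concern?** Only partly. Opposite changes within one preferred term would still cancel. Disagreement shows only where the two ratings of the same event stand together.

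**The case for a change.** The strongest case for a change is that both ratings are already held, the added displays are cheap, and permission to add outputs is not a commitment to do so. That permission is given to the report authors, while the DSMB works from the predefined package. Relatedness also matters beyond the tables: SAP section 7 calls an ad hoc DSMB meeting after one related serious event, or when 6% of vaccinated subjects report related, expected, severe events. It does not say whose rating applies.

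Part of this stands. The supplied documents do not promise a side-by-side display, and a reader might like one. But the DSMB also receives the all-event tables and listing and the serious-event listing and narratives. Protocol 7.10 sends every serious event to the sponsor within 24 hours, with no causality condition. Whose rating drives the DSMB triggers is a separate question, which further tables would not settle. The 2019 note says the outputs were already programmed; the added work would be modest, but no result in hand would be corrected by it.

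**Conclusion.** No change to the plan is needed. Summarising relatedness by the sponsor's final rating is a stated choice, the same in both documents, and following it gives sound adverse event counts. What remains is a preference for extra displays. The SAP already lets report authors add them, and the unseen shells may already contain them. A team that wants more transparency can show both ratings in listings 16.2.7.1 and 16.2.7.2, flag the differences and add one cross-tabulation of investigator against sponsor. Any rating still unresolved can sit in its own row, with a sensitivity count. That is optional reporting detail.

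The effect on any result cannot be sized, because no disagreement rate is documented. The conclusion assumes that investigators replace the provisional codes as Protocol 7.7 requires, and that the sponsor's assessment is complete at lock. If several serious events remained unresolved, a footnote in the report would be enough to show it.
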